8.2 Sample Size Considerations

The primary endpoint is the percentage of patients progressing at 6 months. Based on a contemporary control of no maintenance after best response to prior chemotherapy⁸, the control arm with pembrolizumab alone is expected to have only 8% of patients with no progression at 6 months. To be of clinical interest, at least 58% of patients must be progression-free at 6 months on the pembrolizumab plus paricalcitol arm. A sample size of 12 patients per arm will provide 90% statistical power to detect this difference assuming a one-sided alpha level of 0.05. A one-sided test was selected as we are only interested in the combination if it decreases the percentage of patients progressing at 6 months. This sample size estimate was obtained using binomial enumeration of all possible outcomes to compare two independent binomial proportions (Pearson's chi-squared test) using PASS 15.¹⁸ A statistical concern is that the Pearson chi-squared test does not guarantee the alpha level. We confirmed that we have adequate statistical power using the Miettinen & Nurminen¹⁹ exact likelihood score method (89% power) using Pass 15.

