8.3.6 Analysis of Exploratory Endpoints

8.3.6.1 Comparison of RECIST 1.1 and iRECIST criteria

Given that pembrolizumab is an immunotherapy agent, disease progression will be defined by RECIST and iRECIST criteria (Appendix 5). Comparison of the proportion progression-free at 6 months using iRECIST will be performed using the same method as for the primary endpoint of RECIST 1.1. Additionally, McNemar's Test will be used to estimate the concordance between the two outcome measures.

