3.1. Confirming Progression

Unlike RECIST 1.1, iRECIST requires the confirmation of progression and uses the terms iUPD (unconfirmed progression) and iCPD (confirmed progression). Confirmatory scans should be performed at least 4 weeks, but no longer than 8 weeks after iUPD.

iCPD is confirmed if further increase in tumour burden, compared to the last assessment, is seen as evidenced by one or more of the following:

- Continued increase in tumour burden (from iUPD) where RECIST 1.1 definitions of progression had been met (from nadir) in target, non-target disease or new lesions
 - Progression in target disease worsens with an increase of at least 5 mm in the absolute value of the sum
 - Continued unequivocal progression in non-target disease with an increase in tumour burden
 - Increase in size of previously identified new lesion (s) (an increase of at least 5 mm in the absolute value of the sum of those considered to be target new lesions) or additional new lesions.
- RECIST 1.1 criteria are met in lesions types (target or non-target or new lesions) where progression was not previously identified, including the appearance of additional new lesions.

If iUPD is not confirmed at the next assessment, then the appropriate response will be assigned (iUPD if the criteria are still met, but no worsening, or iSD, iPR or iCR if those criteria are met compared to baseline). As can be seen in table 2, the prior documentation of iUPD does not preclude assigning iCR, iPR, or iSD in subsequent time-point assessments or as best overall response (BOR) providing that iCPD is not documented at the next assessment after iUPD.

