3 ANALYSIS OBJECTIVES

The primary objective is to determine whether combined paricalcitol + pembrolizumab reduces disease progression compared to pembrolizumab alone among patients with stage IV pancreatic cancer who have been put in best response.

The primary endpoint is the percent of patients with radiographic disease progression according to RECIST 1.1 at 6 months.

Secondary objectives include:

- (1) Evaluate the toxicity of the combination of paricalcitol + pembrolizumab versus pembrolizumab alone.
- (2) Evaluate the difference in overall survival in patients administered the combination of paricalcitol + pembrolizumab versus pembrolizumab alone.

Exploratory objectives include:

- (1) Evaluate the difference in disease progression according to iRECIST vs. RECIST 1.1 criteria.

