4 ANALYSIS SETS/ POPULATIONS/ SUBGROUPS

This trial will have 24 patients randomized to paricalcitol + pembrolizumab (n=12) or pembrolizumab alone (n=12). No stratification will be performed.

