5 ENDPOINTS AND COVARIATES

Primary endpoint: Percent of patients with radiographic disease progression according to RECIST 1.1 at 6 months, defined as 180 days from initial treatment (C1/D1).

Secondary endpoints:

- (1) Incidence of toxicities
From initial treatment to end-of-treatment
- (2) Overall survival
Time from initial treatment to death

Exploratory endpoints:

- (1) Disease progression according to RECIST 1.1 versus iRECIST criteria
Percent of patients with radiographic disease progression at 6 months

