Comparison of the proportion of patients who are progression-free at 6 months using iRECIST will be performed using the same method as for the primary endpoint of RECIST 1.1. McNemar's test will be used to estimate the concordance between RECIST 1.1 and iRECIST.

7.2 MEASURES TO ADJUST FOR MULTIPLICITY, CONFOUNDERS, HETEROGENEITY, ETC.

Since all primary and secondary endpoints are pre-specified, there will be no adjustment for multiple comparisons. In the context of a randomized clinical trial, the two treatment arms are expected to be balanced with regard to potential confounders, therefore, adjustment is generally not necessary.

References:

Fine, J. P., and R. J. Gray. 1999. A proportional hazards model for the subdistribution of a competing risk. *Journal of the American Statistical Association* 94: 496–509.

Proposed Tables

Table 1. Characteristics of patients at baseline

Characteristic	Pembrolizumab n = x	Pembrolizumab + Paricalcitol n = x	Total n = x
Age, y			
Median			
Range			
Sex, n (%)			
Female			
Male			
Race/ethnicity, n (%)			
Asian			
Black			
White			
Hispanic			
Other			
Study site, n (%)			
HonorHealth Research Institute			
City of Hope			
Atlantic Health System			
Baylor Scott and White Research Institute			
University of Kansas Medical Center			
Medical College of Wisconsin			
Pancreatic tumor location, n (%)			
Head			
Body			
Tail			
Unknown			
Site of metastatic disease, n (%)			
Liver			
Lung			
Peritoneum			
No. of metastatic sites, n (%)			
1			
2			
3			
>3			

Carbohydrate antigen (CA) 19-9			
Median, U/mL			
Range, U/mL			
Normal (0-35 U/mL), n (%)			
ULN to <59x ULN, n (%)			
≥59x ULN, n (%)			
Previous therapy, n (%)			
Radiation therapy			
Chemotherapy			
Whipple procedure			
Biliary stent			

Figure 1. (A) Progression-free survival by investigator-assessment, (B) Progression-free survival by independent assessment, (C) Overall survival

Table 2. Progression-free survival and overall survival in the intention-to-treat population

Efficacy variable	Pembrolizumab n = x	Pembrolizumab + Paricalcitol n = x	Hazard ratio or Response-rate ratio (95% CI)	P value
Progression-free survival by investigator-assessment				
RECIST 1.1				
Rate of progression-free survival, % (95% CI)				
6 mo				
12 mo				
Median progression-free survival, mo (95% CI)				
Progression-free survival by independent assessment				

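### McNemar's test suits the RECIST 1.1 versus iRECIST difference, but it does not estimate the concordance that both documents promise from it

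*SAP*

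**What the plan says.** SAP 7.1, exploratory outcome 1: "McNemar's test will be used to estimate the concordance between RECIST 1.1 and iRECIST". Protocol 8.3.6.1: "McNemar's Test will be used to estimate the concordance between the two outcome measures". The wording matches, so this is not a slip in one document.

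The objective in SAP section 3 is put differently: "Evaluate the difference in disease progression according to iRECIST vs. RECIST 1.1 criteria". The endpoint in SAP section 5 is "Percent of patients with radiographic disease progression at 6 months", taken under each criterion. Both documents also plan a between-arm comparison of the iRECIST result by the primary method.

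On how the criteria differ, protocol Appendix 5, section 3.1, states: "Unlike RECIST 1.1, iRECIST requires the confirmation of progression".

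No section of either document names percent agreement, kappa, a discordance rate with an interval, or a cross-tabulation for this comparison. The SAP's proposed efficacy table has no iRECIST row.

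**The concern.** The objective asks about a difference and the method sentence promises concordance; these are two questions. McNemar's test addresses the first by asking whether the two kinds of discordant pair are equally frequent. It says nothing directly about how many patients are classified alike, because the concordant pairs do not enter it, and its output is a p-value with no estimate or interval.

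The report would then contain a p-value under the name of concordance. With at most 24 pairs the test has little sensitivity, so a non-significant p is quite possible when a meaningful share of patients change status between criteria. If that p were taken as agreement, the useful number would go unreported: how many RECIST 1.1 progressions do not count under iRECIST.

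**Working it through.** **Inputs from the documents.** There are at most 24 pairs, 12 per arm (SAP section 4). Fewer are possible, because missing values are not imputed (SAP section 6) and some unevaluable patients are excluded (SAP 7.1). The planning progression-free rates are 1/12 and 7/12 (protocol synopsis; 8% and 58% in protocol 8.2).

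The plan gives no figure for this comparison, so there is none to reproduce. The planning rates used in step 3 are consistent with the plan's own power: enumerating all outcomes for 12 per arm gives 90.1%, against the stated 90%.

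**Assumptions.** The documents give no paired counts, so every table below is assumed. They also do not say which version of McNemar's test applies; I use the exact two-sided one and show the alternatives in step 2.

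**Notation.** a = progression by both criteria, b = by RECIST 1.1 only, c = by iRECIST only, d = by neither, N = a+b+c+d.

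- Exact McNemar p: two-sided binomial probability for b out of b+c with probability 1/2.
- Percent agreement: (a+d)/N.
- Kappa: (po − pe)/(1 − pe), where po = (a+d)/N and pe = [(a+b)(a+c) + (c+d)(b+d)]/N².

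**Step 1: what the test can see.** With b = c, p is 1 whatever the agreement:

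| (a, b, c, d) | Exact p | Agreement |
|---|---|---|
| (12, 0, 0, 12) | 1 | 100% |
| (10, 2, 2, 10) | 1 | 83% |
| (4, 8, 8, 4) | 1 | 33% |

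This shows that the statistic is not an agreement measure. The balanced tables with discordance are not a forecast for this trial.

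**Step 2: the pattern to expect here.** If only confirmed progression counts under iRECIST, nearly every iRECIST progression should already be a RECIST 1.1 progression, so c is near 0. With c = 0, p = 2 × 0.5^b and agreement = 1 − b/24:

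| b | Exact p | Agreement | Exact 95% CI |
|---|---|---|---|
| 3 | 0.25 | 21/24 = 87.5% | 67.6% to 97.3% |
| 5 | 0.0625 | 19/24 = 79.2% | 57.8% to 92.9% |
| 6 | 0.031 | 18/24 = 75.0% | 53.3% to 90.2% |

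Up to 5 discordant patients of 24 (21%) stay above a two-sided 0.05.

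The version of the test moves this limit. The uncorrected chi-squared statistic is (b−c)²/(b+c) = b, which passes 3.84 at b = 4, so the limit falls to 3. With the continuity correction the statistic is (b−1)²/b: 16/5 = 3.2 at b = 5 and 25/6 = 4.17 at b = 6, the same limit as the exact test.

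**Step 3: with the planning rates.** Progression by RECIST 1.1 is expected in 11 + 5 = 16 of 24. Assume 5 of these 16 (31%) do not count under iRECIST, giving (11, 5, 0, 8). Then p = 0.0625 and agreement is 79%. For kappa, pe = (16×11 + 8×13)/576 = 280/576 = 0.486, so kappa = (0.792 − 0.486)/0.514 = 0.59.

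**Step 4: what p leaves out.** It does not depend on N. Five one-way discordant pairs give 0.0625 with 24 evaluable patients (79% agreement) and also with 20 (15/20 = 75%).

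Kappa has its own weakness. At the same b = 5 and 79% agreement it is 0.59 for (11, 5, 0, 8), 0.44 for (16, 5, 0, 3) and 0.00 for (19, 5, 0, 0), so it depends heavily on the proportion progressing.

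**The case against.** The strongest reply is that the test fits the objective. Objective and endpoint both concern a difference in progression between criteria, and a paired comparison of two percentages is what McNemar's test is for. That stands. A reader might infer that this exploratory objective would be answered with the wrong quantity; the documents do not support that. The misfit is confined to calling the result an estimate of concordance.

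A reader might also infer from step 1 that the p-value is unrelated to agreement in this trial. That goes too far. With one-way discordance the difference in rates is b/N and agreement is 1 − b/N, so for a fixed N p moves in step with agreement. What remains is that a p-value is not an estimate, carries no interval and does not reveal N.

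The one-way pattern is itself conditional. Protocol 6.1.2.6 asks for a repeat scan after progression by RECIST 1.1 as well as after unconfirmed iRECIST progression. Appendix 5 does leave RECIST 1.1 progression valid without confirmation, so some asymmetry remains. But neither document says whether the 6-month iRECIST endpoint counts unconfirmed or only confirmed progression, or which date applies. It would be an assumption to say that the p-value simply counts progressions unconfirmed by day 180.

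Finally, no section sets an alpha for this test or says that non-significance means concordance. The misreading is a risk to prevent, not something the plan prescribes.

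**Conclusion.** The point holds in a limited form. As written, SAP 7.1 and protocol 8.3.6.1 promise an estimate of concordance that the named method cannot give, and nothing else in the documents supplies one. The paired test of the difference is appropriate and should stay.

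The size, for 24 evaluable pairs, the exact test at a two-sided 0.05, one-way discordance and an iRECIST endpoint that counts confirmed progression: as many as 5 patients (21%) could be classified differently without significance, with agreement anywhere from about 58% to 93% by its interval. The counts are assumed.

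The consequence is low. This is one exploratory comparison; the primary analysis, its alpha and the sample size do not depend on it.

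**What to change.** In SAP 7.1 and protocol 8.3.6.1:

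- Describe exact McNemar as the paired test of equal 6-month progression rates under the two criteria.
- Estimate concordance from the 2x2 table, overall and, descriptively, by arm. Report percent agreement with an exact 95% CI and the number of RECIST 1.1 progressions not counted as progression under iRECIST.
- Optionally add kappa with a CI as a secondary measure, noting its dependence on the proportion progressing.
- State whether unconfirmed or only confirmed iRECIST progression counts at 6 months, since the table cannot be read without it.

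The cost is a sentence or two in each document, plus a small table in the SAP. No new data are needed: protocol 6.1.2.6 already has the investigator and the central radiologist assess disease by both criteria.
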